#### *Wrist-worn wearable devices*

Participants will be asked to wear a wrist-worn device for the duration of follow-up (12 months), which will provide ongoing data collection (summarised in Figure 3 above).

##### **5.8.2.1 Nested wearable comparison study**

A pre-planned pilot phase was conducted to evaluate the feasibility and acceptability of different wearable devices (comparing smartwatches and Fitbits) within the main cohort study. Participants could choose between a Fitbit, an Android smartwatch, or an Apple Watch, depending on their smartphone compatibility. iPhone users could select either an Apple Watch or a Fitbit, while Android users could choose an Android smartwatch or a Fitbit. Those who already owned a compatible device could continue using it. The study monitored device acceptability and data quality, assessing:

1. The most frequently chosen wearable;
2. Participant acceptability after use;
3. The device providing the highest quality data over at least two months.

After six months, we assessed the quality of data collected from pilot study participants, ensuring that each had at least two months of follow-up. We also evaluated the acceptability of the devices used. To account for potential selection bias, we compared participants' baseline data across different

wearables. A predefined set of parameters, outlined in our statistical analysis plan, guided our decision-making for the next steps following the six-month data collection period (see Figure 4). These decision parameters included factors such as

- If one wearable is clearly superior, we will recommend this wearable for the remainder of the cohort.
- If there are no differences between the wearables, we will check for non-inferiority of the Fitbit compared to smartwatch against pre-defined non-inferiority bounds.
- If non-inferiority is established, we will switch to Fitbit as it is the most affordable option.
- If the data is inconclusive (i.e. not superior but also not non-inferior), we will continue to collect data for a further 6 months and repeat analysis based on the *a priori* parameters on all recruited participants with at least 2 months of follow-up time.

Following analysis of the pilot data in January 2025, the Samsung Galaxy Watch was discontinued for the study. This decision was based on several factors: the low quantity and quality of data recorded, the significant resources required to resolve issues with data flow, and the limited metrics provided by the device. In contrast, the Fitbit was retained due to its ability to record a high volume of data, the quality and reliability of the data, and the additional metrics it offers to address the study's primary

[figure not shown]

Figure 4. Nested study examining utility of different types of wearable device

research objectives. However, the Fitbit did not demonstrate non-inferiority compared to the Apple watch. Therefore, the Apple watch was retained due to its high acceptability and uptake among participants, and the additional metrics available over and above the Fitbit in meeting the study's research objectives. As this is a nested study, the dataset gathered from pilot participants will form part of the main cohort dataset.

### **5.8.2.2**

Following the results of the nested wearable comparison, the Samsung Galaxy watch will no longer be offered to participants.

#### *Wearable Device Options for Participants*

##### Participants with iPhones:

- May choose between an Apple Watch or a Fitbit, as both devices are compatible with iOS.
- Participants who already own either an Apple Watch or a Fitbit may continue using their existing device.

##### Participants with Android Phones:

- Will be offered a Fitbit, as it is the only compatible wearable device for Android users.
- Participants who already own a Fitbit may continue using their existing device.

This approach minimises the need for participants to carry two phones and ensures seamless integration of wearable data with their respective smartphones.

Participants who enrolled during the pilot phase or the interim period while awaiting ethical approval for revised study procedures, and are using a Samsung smartwatch, may continue using the Samsung smartwatch for the study duration and keep it, but they will be encouraged to switch to a Fitbit, the only remaining compatible device for Android phones, for the remainder of the study.

### **5.8.3 Clinical measures**

#### *Participants enrolled before mid-January, 2025:*

Participants consented into the study before this time were invited to complete clinical measures at Baseline and every 3 months thereafter (i.e., at 3, 6, 9, and 12 months).

#### *Participants enrolled from mid-January, 2025 onwards:*

Following an approved ethical amendment, participants consented after this date are invited to complete clinical measures at 4 month intervals post-Baseline (i.e., at 4, 8, and 12 months).

#### *Transition Option for Early Participants:*

Participants who consented before the approval of this schedule change will have two options:

1. Continue with the original 3-month assessment schedule, or
2. Re-consent and switch to the updated 4-month assessment schedule for the remainder of their participation in the study.

The schedule of study events outlines when outcomes will be assessed for all participants based on their selected follow-up schedule.

## Clinical measures

Mental Health Status:	Clinical Global Impression-Schizophrenia scale (Haro, et al., 2003) Psychotic Symptom Rating Scales (PSYRATS) distress and frequency scale (Haddock, et al., 1999).
Emotional Distress:	Calgary Depression Scale (Addington, et al., 1990) Fear of Recurrence Scale (FoRSE; (Association, 1994)) Work and Social Adjustment Scale (Mundt JC, 2002) Criticism and Warmth Scale (PCPW) (Hooley, et al., 1989) Dunn Worry Questionnaire (DWQ) (Freeman, et al., 2020)) General Anxiety Disorder Questionnaire (Spitzer RL, 2006) EQ-5D-5L (Herdman, et al., 2011)
Substance misuse:	Alcohol, Smoking and Substance Involvement Screening Test - LITE ( (Ali, et al., 2013); (Ali, et al., 2013))
Service use:	Captured from the medical record; Medication Adherence Rating scale (Thompson K, 2000)
Technology use:	Self-reported acceptability and usability; Post-Study System Usability Questionnaire (PSSUQ; ([name], 2002))

## *Relapse:*

We will use the relapse criteria definition detailed in Appendix R (and is the criteria we used in our NIHR HTA-funded *EMPOWER* trial). We will measure relapse over the 12-months following introduction of the CONNECT app. The criteria for relapse includes:

- i. a return or exacerbation in psychotic symptoms of at least moderate degree, a return or exacerbation of affective symptoms of at least a moderate degree, a return or exacerbation of cognitive disorganisation of at least a moderate degree, a return or exacerbation of excitement of at least a moderate degree, and
- ii. where symptoms were at least one-week in duration, and
- iii. where there is evidence of a decline in functioning or an increase in risk to self or others, and
- iv. there is evidence of an escalating clinical response from services.

Independent and blind observer ratings are applied to detailed extracts taken from clinical notes from a participant's medical record using our detailed Relapse Assessment Protocol (Appendix R) by a research worker at every clinical assessment follow-up time point (this will be date/time-based on case notes of when a relapse occurred in the preceding extraction period and explored during the monthly participant phone call and at the follow-up assessment in the event a relapse is not recorded in the case notes) to identify potential episodes of relapse and exacerbation. These episodes will provide the basis for individual anonymised case vignettes that will be submitted to our independent adjudication panel (comprising members of the research team with the necessary knowledge, experience and skills to make independent blinded judgements regarding relapse/exacerbation) for final confirmation of relapse/not. All vignettes will be fully anonymised.

We will seek consent from participants for access to their medical record throughout the study period to capture key information on relapse and factors including (not limited to) self-harm or suicidal

ideation and service contacts (missed appointments, service use, admissions) to examine other important moderators and predictors of relapse.

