### **5.3 Technical support calls (approx. 15 minutes)**

Previous work by our group has shown that technical issues are more likely to occur early in the use of a DRM system. Therefore, participants will receive follow-up contact (e.g. phone call, text message) weekly for the first four weeks and monthly thereafter to facilitate engagement throughout the study,

provide reminders on how to use the app, remind participants of upcoming outcome assessments, troubleshoot technical difficulties, and discuss any anomalies identified by the study team (e.g. a possible relapse, a serious adverse event). Participants will be provided with an App and Wearable Guide, which includes commonly asked questions and guidance on using the app, wearable and phone. They will be encouraged to contact their local research team with any technical problems that they cannot resolve using the guide. The researcher will work through the problem with the participant, requesting the help of the software team if needed.

Semi-automatic emails / texts will be sent to participants to support engagement and allow people to report issues.

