App development will be supported by a series of PPI consultations. This enables the end users to influence the design and functionality of the app, leading to the development of an app that is more likely to be acceptable and have better uptake. As with our other app builds, by working together, developers and users can learn together and optimise platform functionality, with designers being responsible for pointing out technical options, and users providing information about their needs, practices and how they will use the system. When building the app, working software examples will be delivered and reviewed by the clinical team and advisory groups who will provide interim feedback on the user interface developed, the software performance and its usability. Any changes required are then incorporated into the next iteration of platform development and continue until the fully functioning system is available.

The research team will review the data collected on the CONNECT dashboard at regular intervals and may contact participants if there is a loss of data stream from a device to determine if there are issues relating to functionality or user-experience (and will be a metric of feasibility and acceptability). In the event a symptom question is no longer relevant (e.g. the individual stops hearing voices), or a new symptom emerges (e.g. an individual starts hearing voices), the personalised question set at baseline will be altered.

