#### ***9.1.2. Managing participant distress, risk and disclosures***

During visits, participants will be asked about topics that may be highly sensitive, emotive or distressing topics. There is a small chance that some participants may find the topics upsetting or that they may disclose plans to harm themselves or others. Details of procedures to deal with participant distress and risk disclosures are provided in Appendix H and summarised below.

Participants may become distressed while using the app, phone or wearable device. The CONNECT app will have an emergency contacts section so that, should a participant become distressed while using the app or device, they will be able to contact a relevant organisation. The contact list will include information to out-of-hours emergency contacts (e.g., A&E services; NHS contacts; charity helplines / websites) as well as local organisations that can provide support during business hours. We will also seek consent to contact a participant's care team should they become distressed. We will not, however, monitor the data stream for risk information, to feedback information about a participant's symptom/behaviour pattern, or to intervene in a participant's care.

It is possible that some participants might misinterpret the app to be an emergency device which they can use to communicate information about risk to their care team or to the research team. We will ensure that the app includes a statement that data will not be monitored for information regarding risk and is not an emergency tool. The information sheet will explain that all users should use normal methods of seeking help in a crisis (e.g. calling NHS contacts, the Samaritans or go to A&E) and this information is reiterated in the CONNECT app.

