An essential aim of this project is to determine the feasibility and acceptability of long-term engagement with AMS. By choosing aesthetically appealing, commercially marketed fitness trackers, and by incorporating feedback from our Involvement groups, we hope to minimise stigma and burden for the user and maximise acceptability. However, there may be several factors affecting willingness to use the devices. Participants will be asked to wear the device on their non-dominant wrist for 24 hours a day, ideally taking off only to shower and charge. All devices will be non-invasive, painless, and extremely low risk. They are similar in size and dimension to a watch, manufactured primarily in rubber, and are marked as lifestyle devices, therefore not denoting participation in a research study, reducing stigmatisation and eliminating the possibility of identifying an individual as a research participant. They have been thoroughly tested and approved for safety by regulatory authorities. Participants may however find them to be uncomfortable or cumbersome. They may forget to charge them, or not know how to charge them. The introductory training provided for all participants will mitigate this risk, along with provision of a 'help' section in the smartphone app, and the availability of contact with the research team. The extent to which participants continue to wear the device, or complete the questionnaires on the CONNECT smartphone app is likely to correlate with their mental health; a decline in mood may show itself through disengagement with the research protocol. Regular review of the data by the research team, alongside practices designed to encourage engagement, may help to identify whether a loss of data is due to potential relapse, or technical/practical issues which can be resolved.

The questionnaires to be completed on the CONNECT app have been well-tested in pilot studies and in other research protocols, however the frequency of assessment and usability of the app may make completion of the questionnaires difficult. A member of the research team will contact the participant once a week for the first 4 weeks, followed by monthly contact (e.g. phone call, text message), to mitigate this risk.

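### Relapse adjudication is described as blind, but the protocol lets app and wearable data influence which relapses are looked for, so outcome detection may depend on the predictors

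*Protocol*

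**What the plan says.** Section 5.8.3 (Relapse) has a research worker identify potential episodes from the medical record at each follow-up: "Independent and blind observer ratings are applied to detailed extracts taken from clinical notes". Where the notes are silent, relapse is "explored during the monthly participant phone call and at the follow-up assessment in the event a relapse is not recorded in the case notes". Identified episodes become anonymised vignettes for a panel "comprising members of the research team with the necessary knowledge, experience and skills to make independent blinded judgements regarding relapse/exacerbation". The relapse definition also requires that services stepped up their response (criterion iv). Further detail is deferred to Appendix R, which is not shown.

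Four other statements bear on how episodes come to light:

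- Section 5.8.1: "The research team will review the data collected on the CONNECT dashboard at regular intervals", and may contact participants when a data stream is lost.
- Section 5.3: support calls, weekly for four weeks and then monthly, are used among other things to "discuss any anomalies identified by the study team (e.g. a possible relapse, a serious adverse event").
- Section 9.1.2, on regular data review by the team: it "may help to identify whether a loss of data is due to potential relapse". The sentence gives technical or practical problems as the alternative explanation.
- Section 9.1.2, earlier: "We will not, however, monitor the data stream for risk information".

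The schedules in Appendices 1 and 2 list a check for possible relapse at calls and visits for all participants. Section 6.4.4 describes the Group 2 performance estimates as unbiased.

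**The concern.** In a prediction study the outcome should be found with equal effort whatever the predictors show. Here the people who can see the predictor data are on the team that prompts and explores possible relapses. If a gap in someone's data leads to an additional call, a relapse in that person is more likely to be found than the same relapse in someone whose data look normal. Blinded adjudication cannot correct this, because an episode that was never sought never becomes a vignette.

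The stake is the accuracy of the reported performance. Relapses the model would flag are preferentially found and those it would miss are preferentially lost, so sensitivity looks better than it is. Group 2 uses the same ascertainment, so temporal validation would reproduce the bias. Dating matters too: section 6.4.2 uses a 7-day window for model 1, and an episode uncovered because of a data anomaly could be dated towards that anomaly.

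**Working it through.** **Step 1: trace the route in the text.** Dashboard review (5.8.1) leads to contact when data are lost (5.8.1). Data review is expected to help separate potential relapse from technical causes (9.1.2). Possible relapses identified by the team are discussed in calls (5.3), and relapses missing from the notes are explored in the monthly call (5.8.3). Each link is stated. The protocol does not state the source of the anomalies in 5.3, what raters and panel are blind to, or whether the people finding episodes are masked to device data.

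**Step 2: size of the effect.** The protocol gives no figure to reproduce, so this is an illustration at participant level. Let s be true sensitivity, u the share of true relapses that note review misses, f1 the share of those recovered through contact when the model would flag the participant, and f0 the share recovered when it would not. Assume no false relapse is confirmed and that what the notes capture does not depend on the predictors. Then:

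apparent sensitivity = s(1 − u + u·f1) / [s(1 − u + u·f1) + (1 − s)(1 − u + u·f0)]

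Worked case, s = 0.50, u = 0.10, f1 = 0.8, f0 = 0.3: the 0.50 cancels, giving 0.98 / (0.98 + 0.93) = 0.513.

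All inputs below are assumptions.

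| True s | f1, f0 | Three values of u | Apparent sensitivity |
|---|---|---|---|
| 0.50 | 0.8, 0.3 | 0.10, 0.20, 0.30 | 0.513, 0.527, 0.543 |
| 0.50 | 1, 0 | 0.10, 0.20, 0.30 | 0.526, 0.556, 0.588 |
| 0.60 | 0.8, 0.2 | 0.05, 0.15, 0.30 | 0.607, 0.623, 0.650 |
| 0.60 | 1, 0 | 0.05, 0.15, 0.30 | 0.612, 0.638, 0.682 |
| 0.60 | f1 = f0 | any | 0.600 |

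The rise is about 1 to 5 points in the middle scenarios and 1 to 9 in the extreme ones. It vanishes when recovery does not depend on the data.

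**Step 3: specificity.** Section 6.4.2 makes this the primary criterion. Undetected relapses count as non-relapses. With prevalence π, true specificity c and true sensitivity s:

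- apparent true negatives = (1 − π)c + π(1 − s)u(1 − f0)
- apparent false positives = (1 − π)(1 − c) + π·s·u(1 − f1)

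Take c = 0.90 (assumed), s = 0.60, u from 0.05 to 0.30, and π = 0.25 and 0.40 (section 6.1). Apparent specificity is 0.886 to 0.899 for f1 = 0.8, f0 = 0.2, and 0.901 to 0.907 in the extreme case. It lies between 1.4 points below and 0.7 points above the truth.

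**Step 4: notes as the only label.** Setting f1 = f0 = 0 returns apparent sensitivity to 0.600, but specificity falls to between 0.817 and 0.892, because known relapses are now counted as non-events. A note-only label is therefore informative as a sensitivity analysis but has a cost as the primary label.

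**The case against.** Several points count against a stronger reading, and most of them stand.

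- A reader might infer that the staff who watch the dashboard also extract the notes. The text does not say so: 5.8.1 names the research team, 5.8.3 a research worker, and the study has six sites. Nor does it say that they are kept separate.
- A reader might infer that the blind claim is false. It describes ratings of note extracts and panel judgements on anonymised vignettes. Case-finding upstream that is not blind would limit those ratings without making the statement untrue. Belonging to the research team does not show that a panel member has seen device data, and Appendix R may specify masking.
- The stated trigger for contact is loss of data, not symptom scores, and enquiry about relapse is scheduled for everyone. This limits differential detection, but data-prompted contact comes on top of the scheduled enquiry. Section 9.1.2 itself expects device wear and app completion to track mental health.
- Criterion iv would usually leave a record, and section 6.2.2 expects the outcome to be available from records for almost everyone, so few relapses may be missed. This argues for the low end of the range. The criterion is not wholly separate from study contact, since 9.1.2 has staff liaise with services when risk is identified.
- Direction is uncertain. If the relapses recovered are those with missing data, and the data are then imputed (6.4.2), the model need not benefit unless missingness acts as a predictor.
- Group 2 would contain about 300 × 0.25 = 75 to 300 × 0.40 = 120 relapsers. The standard error of a 50% sensitivity is then √(0.25/75) = 5.8 to √(0.25/120) = 4.6 points, as large as most of the shifts above. That is fair on scale, but a systematic shift is not covered by a confidence interval.
- The statement in 9.1.2 about not monitoring concerns risk, feedback and intervention in care. Checking a lost data stream is different. The real tension is with the later sentence in the same section and with 5.3.

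**Conclusion.** The point holds as a risk that the protocol permits, not as a demonstrated bias. Predictor data can influence which relapses are sought before blinded adjudication begins, in both groups, so the description of the Group 2 estimates as unbiased is not secured by the design as written. The likely effect is upward bias in sensitivity of a few points, with little effect on specificity relative to its true value. These sizes rest wholly on assumed capture and recovery rates, on a participant-level simplification of a rolling 7- or 28-day outcome, and on the model tending to flag the participants who prompt extra contact. The effect on AUC was not calculated. The documents do not establish that performance is inflated, that one person both reviews the dashboard and extracts the notes, or that the blind claim is wrong. The matter is worth correcting because the remedy is cheap and would allow the effect to be measured.

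**What to change.** 1. For every candidate relapse, record how it was first found (scheduled note review, scheduled enquiry at a call or visit, or contact prompted by data) and on what basis its onset was dated. Start promptly, because the route may be hard to reconstruct later.
2. Keep all adjudicated relapses as the primary label. Add a sensitivity analysis of model performance limited to relapses identified from scheduled note review.
3. State that extracts and vignettes contain no app, wearable or engagement information, and that panel members have not seen the participant's dashboard. From now on, where existing staffing allows, have notes extracted by a worker who neither reviews that participant's dashboard nor makes their calls. If Appendix R already says this, repeat it in 5.8.3.
4. Reconcile sections 5.3, 5.8.1 and the later part of 9.1.2 with 5.8.3 and the earlier statement in 9.1.2, so that the protocol says consistently what the data are reviewed for.

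The cost is one database field, one extra analysis and some swapping of caseloads, with no additional assessors. Extractions already completed cannot be masked retrospectively.
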